9.3.1.1 Informed Consent

Informed consent must be obtained from each candidate before any data is collected.

Purpose: Extensive efforts should be made to inform candidates fully of all aspects and obligations of the study, the risks and benefits and the randomization odds.

Procedure: After the candidate has had the opportunity to discuss the study with clinic personnel and have any questions answered, she will be asked if she wishes to participate in PRIDE. She will be asked to read, fill out, sign and date the PRIDE Informed Consent Form in accordance with Federal Regulations and the guidelines set by local Institutional Review Boards (IRBs). Inform the participant that we are required by federal law to obtain fully informed consent for each aspect of the trial. Encourage the participant to ask questions if she does not understand any aspect of the form. It is very important that the participant is fully informed and enters the study freely and with a clear understanding of all study requirements.

Informed Consent Forms must be approved by local IRB prior to the start of the study. The original signed form should be filed in the participant's study binder and a copy should be given to the participant.

A copy of each clinic's approved Informed Consent Form and local IRB

approval will be kept on file at the Coordinating Center.

9.3.1.2 HIPAA

Purpose: The Health Information Portability and Accountability Act (HIPAA) requires that research participants give authorization for use of protected health information (PHI), defined as identifiable private information from medical records.

Procedure: Please follow the HIPAA procedures as defined at your institution. The original signed HIPAA form should be filed in the participant's study binder.

9.3.2 The Two Incontinence Questionnaire (2IQ)

This is a one page, 2-item, self-administered questionnaire designed to diagnose the type of urinary incontinence experienced by the participant. The accuracy of this brief questionnaire is being tested versus extensive medical assessments in a concurrent urinary incontinence trial. This questionnaire should be completed early in the study before the participant receives any training or information about incontinence.

The introductory, unnumbered question checks that the participant has leaked some urine in the last 3 months. If the response is "No" the participant is not eligible for the study and the coordinator should review the Eligibility Screening form to check for erroneous information about current incontinence.

Questions #1 and #2 can have multiple responses. Participants are asked to fill in all bubbles that apply. When this is completed the form should be reviewed at the clinic and faxed to the Coordinating Center data system.

9.3.3 7-Day Voiding Diary

The 7-day Voiding Diary will be collected once during Screening to determine eligibility, then again at the Randomization Visit, and at Months 6, 12 and 18. This diary is a primary outcome measurement for PRIDE and it is extremely important that the participant understands how to fill out the diary.

Two versions of the voiding diary are available – a short and a long version. The long version should be given to all participants initially. It allows for the

recording of up to 40 episodes of urinary incontinence daily and has one extra page at the back. The shorter version allows for the recording of up to 18 episodes daily and has two extra pages at the back. The short version may be used when the initial diary has been reviewed and it seems unlikely that the participant will need space provided by the long version.

Every effort should be made by study staff to encourage participants to fully complete all diary information and bring the diary to the next visit. Suggest that the participant carry the diary with her every day for seven days. If she is unable to do this suggest that she record her episodes on a piece of paper and transcribe them at the end of the day.

Staff will hand write Subject ID # and acrostic on *every* diary day page. Use the instructions on the inside cover of the diary to explain, in detail, diary entry procedures to the participant. For 7 days, she should record every time she urinates in the toilet and leaks urine.

Using a calendar, mark the scheduled date of the participant's Screening Visit 1 and arrange a mutually agreeable start date for the diary, keeping in mind that she must start it at least 8 days prior to the next study visit. We recommend that the participant start the diary *the morning after* she receives it. If this is not feasible discuss with the participant an alternate day to start the diary. Ideally she will fill the diary out daily for 7 consecutive days and bring it back to the next visit. If she forgets a day, instruct her to continue recording beginning the day after the one she forgot and to finish 7 complete days.

Written instructions for how to fill out the diary are included at the beginning of the diary and in Appendix 9A. Appendix 9A includes a sample reminder letter for participants also. Ask the participant to strike through "Page 2" any time she does not need these extra spaces. This will make it easier for you and she to review the diary later.

Review the symptoms of "Urge" vs "Stress" incontinence with the participant. Tell her to mark "Other" only if her leaking episode doesn't seem to fit either Urge or Stress. Ask her to describe very briefly in column 4, what she was doing when she leaked urine, especially if she marks "Other". She does not have to write in column 4 if she urinates in the toilet without leaking. Explain that you will review her diary with her when she returns. Tell the participant that she can call the Study Coordinator to ask questions while completing the voiding diary. When you are finished explaining the diary:

- determine if the participant has any questions about how to complete the diary
- provide a couple of hypothetical scenarios and ask her to tell you how she would record these in the diary
- remind the participant to bring the completed diary with her to the next visit
- if she can't start the diary the next morning, make a note of when she plans to start and call her the day before to remind her that she is to start the diary the next day

Occasionally, it can be a challenge for the participant to identify the type of incontinence episode she has experienced. Here are some examples that may be helpful:

1. Leaking upon standing up – this may be a urine flow that hasn't quite finished (not an incontinent episode), pressure on the bladder when standing (stress incontinence), or a sudden need to urinate again (urge incontinence). It is important to have the participant describe the episode in as much detail as possible to help her determine the nature of the leaking.
2. Leaking when sleeping - this may occur when obese participants roll over and put pressure on the bladder (stress) or because they have dreamt they are on the toilet (urge). Probe for as much information as possible. If most other episodes marked on the diary are urge episodes it is likely that bed-wetting is also. Note that a report of "waking up wet" is an episode that should be recorded on the diary for the previous night.
3. Leaking on the way to the bathroom is usually urge incontinence. Hearing or feeling water often creates urge.
4. Leaking described as "just had to go" is usually urge incontinence.

9.4 SCHEDULING SV1

At the end of the OV, a Screening Visit 1 should be scheduled to take place at least 8 days after the Orientation Visit (to allow time to complete the 7-day Voiding Diary) but no longer than 9 months from the Eligibility Screening (ES) date (see Ch.9.4.1).

The participant should leave the Orientation with the following packet of forms to fill out at home:

- Contact Information/Physician Forms (local)
- Demographics Form (if not completed in clinic)
- 2IQ (if not completed in clinic)
- 7-day Voiding Diary

9.4.1 SV1 DELAYED FOR NEXT COHORT

If the SV1 is scheduled more than three months after Eligibility Screening to facilitate the formation of intervention groups, then the Eligibility Screening Form must be reviewed and eligibility information must be updated as necessary before the SV1 takes place. **The participant keeps the same ID number.** The participant may be invited back for a refresher Orientation.

If a participant attends an Orientation Visit, completes the 2IQ and Demographics form, and then is held for the next cohort:

1. Post a query to Q30 on the Eligibility Screening Form
 - Select "Pending" and indicate "Day Group" or "Night Group"
2. Indicate on the Participant Tracking Log that the candidate is waiting for the next cohort.

When screening begins for the next cohort, eligibility items (weight, weight loss, exclusionary medications, etc) should be reviewed with the candidate, if three or more months have passed. If information has changed slightly but does not change eligibility status, you do not have to make any changes to the ES form. If the candidate is still eligible, she can attend an Orientation Visit again or schedule Screening Visit 1. The candidate does not have to complete the 2IQ or Demographics form again.

If the candidate is no longer eligible when the Eligibility Screening form is reviewed, post queries and edit the information that has changed. Post a query again to Q30, select "Ineligible" and enter the number of the question that now makes the candidate not eligible for PRIDE.

For more details, please review the "Guidelines for Delayed Screening Schedules in PRIDE" attached as Appendix 9B.

How to Complete this Diary**When to start the diary:**

- Begin recording information **when you get up for the day**.
- If you wake up during the night or early morning (before you get up for the next day), continue recording on the diary day that you have already started.
- Begin a new diary day each morning when you get up for the day.

How to complete the diary:

- Record the day of the week and the date you started the diary.
- Record the time when you got up for the day.
- At bedtime, record the time you went to bed for the night.
- After completing the diary day, indicate whether you recorded each time you urinated or leaked.

How to record when you urinate or leak:

- "TIME" **Write the time each urination occurred. Be sure to check (√) the AM or PM box.**
- "DID YOU URINATE IN THE TOILET?" Check (√) yes if you urinated in the toilet at all. This may or may not include leakage.
- "DID YOU LEAK URINE?" Check (√) yes if you leaked urine of any amount. Leakage could range from a few drops to a large accident.
 - NOTE: There may be instances when you need to check (√) Yes for #2 AND #3 on the same entry.
- 3a. "REASON FOR LEAKAGE" If you check (√) yes on the column, "DID YOU LEAK URINE?" you should **always** indicate the **main** reason for the leakage by checking only **one** of the three boxes in the next column labeled, "**REASON FOR LEAKAGE.**"

"Urge"	Check (√) this box if you leaked because you felt an urge or pressure to urinate and felt that you couldn't make it to the bathroom on time .
"Stress"	Check (√) this box if you leaked because of coughing, sneezing, laughing, lifting something heavy, moving too quickly, or other physical activity.
"Other"	Check (√) this box if you had urine leakage that was not an "Urge" or "Stress" leakage.
- "WHAT WERE YOU DOING?" Please write down what you were doing at the time of this episode, for example, running, coughing, or cooking.

If you run out of room on your diary:

- Each diary day has two pages. If you run out of room on Day One, page 1, go to Day One page 2. If you run out of room on Day One, page 2, use the "EXTRA ENTRIES" page at the back of the diary.
- When using the "EXTRA ENTRIES" page, please write the date when each urination occurred. Note that this "EXTRA ENTRIES" page can be used for all seven diary days.

IF YOU HAVE ANY QUESTIONS PLEASE CALL _____

Appendix 9B

Guidelines for Delayed Screening Schedules in PRIDE

As of October 28, 2004, the maximum allowed interval between the Eligibility Screening interview and the randomization visit has been extended to 9 months. There will be no restrictions on the intervals between the Eligibility Screening, OV, SV1, SV2 and RV. These changes facilitate the accumulation of groups for intervention sessions. The extension of screening time does not change the entry criteria for the study. Eligibility criteria should be reviewed periodically as follows:

- A. If the interval between Eligibility Screening(ES) and Orientation Visit (no other forms completed) is more than 3 months, all questions on the Eligibility Screening Form (ESF) must be reviewed with the candidate before proceeding with further visits. The interviewer should post queries for the ESF and update Q.30 as necessary.
- B. If the candidate has completed one or more screening visit forms (apart from the ESF) AND the duration between Screening Visit 1 and Randomization Visit is more than 3 months, the following items must be rechecked:

Check if done:	Recheck:	Form:	Action:
	Body Mass Index (BMI)	Review Eligibility Screening Form (ESF) Question 10 with the candidate.	If Height and Weight form was already completed AND the candidate's BMI is now out of range, she is still eligible. Continue with screening. If Height and Weight form was not completed AND the candidate's BMI is now out of range, she is not eligible. Complete the Inclusion/Exclusion Form and mark "No" for criteria 1B.
	Weight loss of 10 pounds or more	Review ESF Question 11 with the candidate.	If candidate has lost 10 pounds or more in the last 3 months, she is not eligible. Complete the Inclusion/Exclusion Form and mark "Yes" for exclusion criteria 2B.
	Weight loss	Review ESF	If candidate has started a weight loss

	program	Question 16 with the candidate.	
program AND is willing to stop, no action is needed.
 
If candidate has started a weight loss program AND is not willing to stop, complete the Inclusion/Exclusion Form and mark "Yes" for exclusion criteria 2B.

	Medications	Review ESF Question 17 with the candidate to check for new medications.	
If candidate has started a weight loss or incontinence medication AND is willing to stop, no action is needed.
 
If candidate has started a weight loss or incontinence medication AND is not willing to stop, complete the Inclusion/Exclusion Form and mark "Yes" for exclusion criteria 2A.
 
If the Medications Form was completed and the candidate has new medications, the Medications Form should be updated by posting a query.

	New diagnosis or medical condition	Review ESF Questions 8, 15, 19, 21-26 and Health History Form Questions 16a-16g with the candidate.	
If the candidate is not eligible, do not post queries to the ESF or Health History Form.
 
Complete the Inclusion/Exclusion Form as follows:
 
If candidate is not eligible because of:
 
ESF Q.8 ☉ mark "Yes" for exclusion criteria 2C.
 
ESF Q.15 ☉ refer candidate for treatment. She is eligible to continue screening after treatment.
 
ESF Q. 19 ☉ mark "Yes" for exclusion criteria 2F.
 
ESF Q. 21 ☉ mark "Yes" for exclusion criteria 2H.
 
ESF Q. 22 ☉ mark "Yes" for exclusion criteria 2H.

			
ESF Q. 23 ☉ mark "Yes" for exclusion criteria 2H.
 
ESF Q. 24 ☉ mark "No" for inclusion criteria 1J.
 
ESF Q. 25 ☉ mark "No" for inclusion criteria 1J.
 
ESF Q. 26 ☉ mark "Yes" for exclusion criteria 2I.
 
HHx Q.16a-16g☉ mark "Yes" for exclusion criteria 2E.

	Participation in a research study	Review ESF Question 28 with the candidate.	If the candidate is not eligible, complete the Inclusion/Exclusion Form and mark "Yes" for exclusion criteria 2J.

CHAPTER 10

SCREENING VISITS

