8.7.16 Questions 16 and 16a

If the candidate is not in an intensive weight loss program, mark the bubble “No”, do not answer 16a, but proceed to question 17. **Long-term weight loss maintenance programs, such as Weight Watchers, Take Off Pounds Sensibly (TOPS), or Overeaters Anonymous (OA) are not considered “active” weight loss programs and do not exclude the candidate.** If the candidate is in one of these or similar long term weight loss maintenance programs you should mark “No” to this question and proceed to question 17.

If the candidate is enrolled in an intensive weight loss program mark the “Yes” bubble and go to question 16a. If the candidate is enrolled in a short-term, active or intensive weight loss program, it will be impossible to evaluate the effects of PRIDE’s weight loss intervention. Therefore, candidates must be willing to stop any current intensive weight loss program in order to qualify for PRIDE.

It is important to ascertain whether the candidate is in a weight loss program that is prescribed and monitored by a health care provider. In this case, even if she is willing to stop, she must obtain a letter of agreement from that health care provider that she can stop her current program for approximately 22 months. In such cases, continue screening but note on the Participant Tracking Log that a “clearance to participate” letter must be obtained prior to Randomization. Tell the candidate you will mail her some information and a form for her health care provider to sign and fax to the PRIDE site.

If the candidate is enrolled in a self-initiated active weight loss program and is willing to stop, she can continue screening. However, a note should be made on the log sheet to confirm during the Screening Visits that the weight loss program has been discontinued.

As mentioned earlier, the investigator may choose to avoid screening women who have participated in intensive weight loss programs at her/his clinical site within the past 5 years since the intervention materials will be too similar. Please document the number of candidates who are not suitable study candidates due to previous participation in local intensive weight loss programs and provide these numbers to the Coordinating Center at the end of enrollment.

8.7.17 Question 17

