8.7.19 Question 17b

If the candidate is willing to stop her prescription medication she must first call the prescribing physician, obtain a letter of agreement and discontinue the

medication under the physician's guidance. If the candidate is willing to do this, offer to mail her information and a form for the physician to sign and fax to the PRIDE site. Make a note on the Participant Tracking Log that the medication must be discontinued and a letter received from the health care provider by the time of the randomization visit.

If the candidate is not willing to stop the prescription medication that she is taking for weight loss or incontinence she is not eligible for PRIDE. Fill in the bubble "No" and skip to question 30.

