10.6 SCHEDULING THE RANDOMIZATION VISIT

The Randomization Visit should take place within 4 weeks of SV2.

Participants who are still eligible should leave the clinic with the following items:

- An appointment for the randomization visit
- 7-Day Voiding Diary #2
- 24-hour Pad Test Kit

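### The manual drops the protocol's one-month limit on incontinence and weight-loss drugs, and Appendix 9B's re-check conflicts with the stopping steps in 8.7.16 and 8.7.19

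*Protocol*

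**What the plan says.** **Protocol.** Section 6.3, exclusion 1, covers both present use and use in the preceding month. Its footnote allows a woman to be screened again one month after she stops.

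**First screening, drugs (8.7.19).** A woman willing to give up a prescribed incontinence or weight-loss drug may continue, but "she must first call the prescribing physician, obtain a letter of agreement and discontinue the" drug under that physician's direction. Staff note on the tracking log that "the medication must be discontinued and a letter received from the health care provider by the time of the randomization visit".

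**First screening, programs (8.7.16).** If a provider prescribes and monitors the program, "she must obtain a letter of agreement from that health care provider that she can stop her current program for approximately 22 months". If she began it herself, staff log it and confirm at the screening visits that it has ended.

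**Delayed screening (Appendix 9B).** When more than three months separate Screening Visit 1 (SV1) from the Randomization Visit (RV), staff go back over Questions 16 and 17. For drugs the outcome is "If candidate has started a weight loss or incontinence medication AND is willing to stop, no action is needed". For a newly started weight loss "program AND is willing to stop, no action is needed". The same appendix states: "The extension of screening time does not change the entry criteria for the study".

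**Checklist (Appendix 12A).** Exclusion item A asks whether she is on such therapy at present. It says nothing about the preceding month, and no item asks for the provider's letter.

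**The concern.** In both places the manual departs from a rule the sponsor had already written.

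First, staff who complete the checklist correctly can randomize a woman whom exclusion 1 rules out. The second voiding diary and the pad test, which supply the baseline for the primary outcome and for a secondary outcome, may then reflect a treatment she has just ended.

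Second, a coordinator who follows the Appendix 9B row literally does not ask for the prescriber's agreement before a prescribed drug is stopped. Chapter 8 treats that agreement as mandatory for the same question and the same answer.

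**Working it through.** No figure in the plan is at issue. The check compares texts and adds a short timing calculation.

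**1. Does any manual step restore the one-month limit?**

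| Step | What it tests |
|---|---|
| 8.7.17, Question 17 | drugs being taken now |
| 8.7.19 | stopped by RV |
| 10.4.2.3, Medications Form | drugs being taken at the review |
| 15.2 | use at baseline |
| 12.3.6 | drugs started since the last visit |
| Appendix 12A, item A | current use |

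None asks about the previous month, so nothing in the manual makes up for the gap in item A.

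**2. What the gap allows.** Let RV be day 0 and take a month as 30 days (an assumption). The pad-test instructions in 10.4.2.8.1 require the diary to start at least 8 days before the visit, so its latest position is days −8 to −2. The pad test falls within diary days 4 to 7, that is, days −5 to −2.

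- Last dose on day −1: item A is passed, and 7 of 7 diary days are on drug.
- Last dose on day −31 (30 drug-free days before RV): 0 of 7 diary days are on drug.

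**3. What the medication review catches.** Under 10.4.2.3, a woman on a listed drug at Screening Visit 2 (SV2) is ineligible. Two routes remain.

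- *On treatment.* Section 15.0 lets medications be recorded at SV1 instead. On the delayed route, the drug may also be started after the review.
- *Just after treatment.* Suppose her last dose is the day before SV2 and she starts the diary the next morning, as 9.3.3 recommends. The shortest workable gap then puts SV2 on day −9 and the last dose on day −10. The diary on days −8 to −2 runs from 2 to 8 days after the last dose. She passes both the review and item A, yet is 10 days off therapy where exclusion 1 asks for a month.

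**4. Would enforcing the month be enough?** Let the SV2-to-RV gap be G days, with the diary starting the morning after SV2, on day −(G − 1). With the last dose on day −31, the diary has no on-drug days when G − 1 ≤ 30, that is, G ≤ 31. The target in 10.6 is four weeks (G = 28, diary starting on day −27), so the one-month rule alone covers it.

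**5. Appendix 9B against Chapter 8, for a woman willing to stop.**

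| Situation | Chapter 8 | Appendix 9B |
|---|---|---|
| Prescribed drug | prescriber called, letter, supervised stop, log note | no action |
| Provider-monitored program | letter, log note | no action |
| Self-initiated program | log note, stop confirmed | no action |

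The Medications row of Appendix 9B also asks for an already completed Medications Form to be updated by query. That records the new drug. It does not confirm the stop or produce a letter.

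**The case against.** **The Appendix 9B entry may concern forms only.** Its counterpart, for a woman unwilling to stop, is to complete the Inclusion/Exclusion Form. Section 10.7 reserves that form during screening for women who have become ineligible, and 9.4.1 says small changes that leave eligibility intact need no edit to the screening form. On this reading the entry means only that no ineligibility is recorded, and Chapter 8 still governs Questions 16 and 17. This is possible, but the appendix does not say so. The same column contains steps that are not form entries, such as sending a woman with a urinary infection for treatment.

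**Physician consent is obtained elsewhere.** The visit schedule in 8.1 places it at SV1 or SV2. A drug started after those visits would not have been considered, and consent to take part is not the prescriber's agreement to stop a drug.

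**The final gate holds.** Section 12.3.6 requires every exclusion item to be answered no, item A stops a current drug user, and item B stops a woman in an active program. This stands. For self-initiated programs it leaves almost nothing of the conflict.

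**Few women are exposed.** Checklist item G, documented by the signed consent, is an agreement not to start new treatment. This stands for the Appendix 9B route. It does not help with a woman already on a drug at first screening who stops under 8.7.19.

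**The two interval rules.** A reader might infer that "The Randomization Visit should take place within 4 weeks of SV2" contradicts "There will be no restrictions on the intervals between the Eligibility Screening, OV, SV1, SV2 and RV". It need not: the first is a target, the second says no interval is mandated, and both can hold.

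**Conclusion.** The concern holds, as a minor one. The omission in item A and 8.7.19 is plain on the text. The Appendix 9B conflict is there on its face, although a milder reading is available. What can be lost is the prescriber's agreement and the one-month washout.

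Three stronger conclusions are tempting, and the documents do not support them:

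- *Women are randomized while on an excluded drug.* The checks at RV are written to stop this.
- *The treatment comparison is biased.* All of this happens before assignment, so any disturbance of the baseline falls on both arms alike.
- *Power suffers measurably.* The documents give no count of women who would take this route, so no loss can be computed.

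The size is therefore given only per woman: between 0 and 7 of 7 baseline diary days on drug, depending on when she stops. This assumes a 30-day month and the diary timing in 10.4.2.8.1. That the number of women is small is a judgement based on item G and the RV checks, not a figure in the documents.

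**What to change.** - Appendix 12A, item A: extend it to any use in the month before randomization, matching exclusion 1.
- Section 8.7.19: require the drug to be stopped at least one month before RV, instead of by RV.
- Appendix 9B, weight-loss program and medication rows: replace both no-action entries with an instruction to follow 8.7.16 or 8.7.19.

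A separate rule to repeat the diary and pad test is not needed. Exclusion 1 does not ask for one, and the one-month limit alone keeps the diary free of on-drug days when the four-week target in 10.6 is met.

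The cost is four short edits to the manual. A few women may wait up to a month or move to a later wave. One already near the nine-month limit in 4.3.3 would have to be screened again.
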